### 3.2.2 Dose Escalation (Part 1)

The objective of the Dose Escalation phase is to determine the MTD and/or RP2D of H3B-6527 in subjects with advanced HCC. Intrahepatic cholangiocarcinoma (ICC) subjects were also enrolled from protocol Amendment 5 to Amendment 7.

For dose-escalation purposes, toxicities assigned as DLTs during the first cycle will be assessed. After 3-6 subjects in a cohort have completed Cycle 1 (C1), all available safety data will be reviewed by the Safety Review Committee (SRC) consisting of Sponsor personnel and investigators and the decision to proceed to the next dose cohort will be made jointly. Toxicities will be graded using the National Cancer Institute (NCI) Common Terminology Criteria for Adverse Events (CTCAE) version 4.03.

Once a subject has completed C3 at the initially assigned dose schedule and dose level (QD or BID), intrapatient dose escalation will be allowed.

H3B-6527 will be tested in sequential escalating dose cohorts (n=3 to 6) at the dose levels listed in the Table 1.

**Table 1 Dose Cohorts in H3B-6527 Dose Escalation Phase**

Dose level	Initial No. of Subjects	H3B-6527 Total Daily Dose
-1	3	150 mg
1 a	3	300 mg
2	3	600 mg
3	3	1000 mg
4	3	1400 mg
5	3	2000 mg

These total daily (dose levels may be evaluated in QD or BID) dose schedules, including intermediate levels, differing MTDs by sub-population (e.g., disease indication or ethnicity), and in expansion of an existing dose level up to 12 evaluable subjects following discussion between the Sponsor and the investigators, if supported by evolving safety, tolerability, PK, and pharmacodynamic data.

a: Planned starting dose level in QD schedule.

Subjects will be assigned to a dose level in the order of study entry. Initially, 3 subjects will be enrolled at the starting dose level. If 2 of the 3 subjects experience a DLT then the dose level -1 (150 mg) will be explored. If 1 of the 3 subjects experiences a DLT then the dose will be expanded to 6 subjects. If  $\geq 2$  of 6 subjects in the starting dose cohort experience a DLT during the first cycle, then the dose level -1 (150 mg) will be explored.

Dose escalation to the next higher dose may proceed if no DLT is observed in C1 among the first 3 subjects accrued to a cohort. If 1 of 3 subjects in the cohort experienced a DLT, up to a total of 6 subjects will be enrolled. If 2 or more of the 3-6 subjects in a cohort experience a

DLT, dose-escalation will cease, and additional subjects will be treated at a lower dose level. Dose escalation will continue until a dose level where 2 or more of 6 subjects experience a DLT.

To be evaluable for a DLT, subjects must have completed safety assessments through predose on C1 Day 1 and must have received at least 17 of 21 (80%) study days within C1, unless due to a DLT. Subjects who discontinue from the study for reasons other than DLT before completing C1 are to be replaced.

### Definitions of DLT and MTD

The DLTs are defined as any of the toxicities listed in Table 2 occurring during C1 and judged by the investigator as related to study drug (i.e., assessed as unrelated to disease, intercurrent illness, or concomitant medications).

**Table 2 Dose-Limiting Toxicity Definition**

TOXICITY	CRITERIA
Hematology	
 
• Febrile neutropenia
 
• CTCAE Grade 4 neutropenia that does not resolve to Grade <math>\leq 2</math> within 7 days
 
• CTCAE Grade 3 thrombocytopenia requiring transfusion
 
• CTCAE Grade 3 thrombocytopenia and clinically significant bleeding
 
• CTCAE Grade 4 thrombocytopenia
 
• CTCAE Grade 3 anemia if transfused or if lasting for more than 7 days
 
• CTCAE Grade 4 anemia of any duration
 

Gastrointestinal	
 
• CTCAE Grade 3 nausea, vomiting and/or diarrhea lasting more than 72 hours despite the use of optimal anti-emetic/antidiarrheal treatment
 
• CTCAE Grade 4 diarrhea and/or vomiting irrespective of prophylaxis or appropriate treatment
 

Renal	
 
• CTCAE Grade <math>\geq 3</math> serum creatinine
 

Hepatic	
 
• CTCAE Grade 3 bilirubin (<math>>3.0 \times</math> the upper limit of normal (ULN)) and/or alanine aminotransferase (ALT) <math>\geq 10 \times</math> ULN
 
• For subjects with a starting ALT within the normal range for the local laboratory, an elevation ALT <math>\geq 5 \times</math> ULN for the local laboratory
 
• For subjects with an abnormal value <math>\geq</math> ULN at baseline based on the local laboratory ranges, an ALT elevation <math>\geq 10 \times</math> ULN for the local laboratory
 

Other AEs not listed above	
 
• Non-hematologic toxicities of CTCAE Grade <math>\geq 3</math> except for the following. 
 
- CTCAE Grade 3 fatigue lasting less than 1 week,
 
- Isolated CTCAE Grade 3 elevations in biochemistry laboratory values without associated clinical symptoms that last for <math>\leq 7</math> days. This includes electrolyte abnormalities that respond to medical intervention.
 
 
 
• H3B-6527-related, CTCAE Grade 2 nonhematologic toxicities that, in the opinion of the treating investigator, require a dose reduction or discontinuation of study drug, or lead to the subject's failure to complete at least 17 days of study drug administration in C1, may be deemed to be
 

	dose-limiting if agreed upon by participating investigators and the Sponsor.
--	--

AE = adverse event, ALT = alanine aminotransferase, AST = aspartate aminotransferase, C = Cycle, CTCAE = Common Terminology Criteria for Adverse Events, ULN = upper limit of normal.

The MTD is defined as the highest dose at which no more than 1 of 6 subjects experiences a DLT in the dose cohort. (Note that at least 6 subjects must be treated at the dose level potentially considered to be the MTD before that dose level can be considered the MTD).

The RP2D may not exceed the MTD and will be agreed upon by the SRC based on an integrated evaluation of safety, tolerability, clinical benefit, PK, and pharmacodynamic data, for all dose levels tested. Clinically significant toxicities (eg, chronic Grade 2 toxicities) or adverse events (AEs) that meet the definition of dose limiting but occurring after C1 (dose modifying events, DME) may be considered when determining the RP2D. Once the MTD/RP2D is reached, at least 6 HCC subjects must be enrolled at the RP2D (regardless of the total number of subjects enrolled at that dose level) in order to proceed with dose expansion.

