Hematology	
• Febrile neutropenia• CTCAE Grade 4 neutropenia that does not resolve to Grade ≤ 2 within 7 days• CTCAE Grade 3 thrombocytopenia requiring transfusion• CTCAE Grade 3 thrombocytopenia and clinically significant bleeding• CTCAE Grade 4 thrombocytopenia• CTCAE Grade 3 anemia if transfused or if lasting for more than 7 days• CTCAE Grade 4 anemia of any duration
Gastrointestinal	
• CTCAE Grade 3 nausea, vomiting and/or diarrhea lasting more than 72 hours despite the use of optimal anti-emetic/antidiarrheal treatment• CTCAE Grade 4 diarrhea and/or vomiting irrespective of prophylaxis or appropriate treatment
Renal	
• CTCAE Grade ≥ 3 serum creatinine
Hepatic	
• CTCAE Grade 3 bilirubin ($>3.0 \times \text{ULN}$) and/or AST/ALT $\geq 10 \times \text{ULN}$• For subjects with a starting AST/ALT within the normal range for the local laboratory, an elevation AST/ALT $\geq 5 \times \text{ULN}$ for the local laboratory

Table 2 Definition of Dose-Limiting Toxicity (Cycle 1 Phase 1 Only) or Dose-Modifying Event (Cycle 2 or Beyond and Any Cycle in Phase 2)

TOXICITY	CRITERIA
	
 For subjects with an abnormal value \geq ULN at baseline based on the local laboratory ranges, an AST/ALT elevation $\geq 10 \times$ ULN for the local laboratory
Other AEs not listed above	
 Nonhematologic toxicities of CTCAE Grade ≥ 3 except for the following: 
 CTCAE Grade 3 fatigue lasting less than 1 week Isolated CTCAE Grade 3 elevations in biochemistry laboratory values without associated clinical symptoms that last for ≤ 7 days. This includes electrolyte abnormalities that respond to medical intervention. H3B-6527-related, CTCAE Grade 2 nonhematologic toxicities that, in the opinion of the treating investigator, require a dose reduction or discontinuation of study drug, or lead to a failure to complete at least 17 days of study drug administration in C1, may be deemed dose-limiting if agreed upon by the participating investigator and the Sponsor.

AE = adverse event, ALT = alanine aminotransferase, AST = aspartate aminotransferase, C = Cycle, CTCAE = Common Terminology Criteria for Adverse Events, ULN = upper limit of normal.

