As described in [Table 2](#), any subject with an increase in alanine aminotransferase (ALT) or aspartate aminotransferase (AST) to $\geq 2 \times$ the baseline value or with a bilirubin level of $> 3 \times$ the upper limit of normal (ULN) must have repeat testing 1 week later. If either the ALT or bilirubin level increase further, testing will be repeated at 1-week intervals until the values return to baseline levels.

The only instance in which the AST/ALT and/or bilirubin changes will not be considered a DLT is if there is unequivocal evidence that these increases are due to progression of the underlying disease or the intrahepatic malignancy. In these cases, determination of a non-DLT event will be made jointly by the Sponsor and the investigator(s).

For any dose-limiting hepatic toxicity that does not return to baseline within 7 days, an abdominal computed tomography (CT) scan must be performed to assess whether it is related to disease progression.

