### 3 INTRODUCTION

This Statistical Analysis Plan (SAP) describes the planned statistical analysis and reporting for Clinical Study Protocol *H3B-6527-G000-101* titled “An Open-Label, Multicenter Phase I Study to Evaluate the Safety, Pharmacokinetics and Pharmacodynamics of H3B-6527 in Subjects with Advanced Hepatocellular Carcinoma”.

This SAP amendment is based on SAP Amendment 0.1 dated on 08 Nov 2017 and the protocol Amendment 09 dated on 30 Sep 2020. In the event of future amendments to the protocol, this SAP amendment will be modified to account for changes relevant to the statistical analysis.

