# 7 CHANGES IN THE PLANNED ANALYSES

SAP Amendment 0.1: DLT analysis set is defined for the evaluation of DLTs.

SAP amendment 0.2: Efficacy summaries will only include HCC subjects. Efficacy listings will include both HCC and ICC subjects who were enrolled prior to Protocol Amendment 8.

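### SAP Table 2 keeps an ALT-only hepatic DLT definition although the protocol version it is based on counts AST or ALT, so the reported DLT/MTD table could disagree with the dose-decision record in either direction

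*SAP*

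**What the plan says.** SAP Section 3 states its base: "This SAP amendment is based on SAP Amendment 0.1 dated on 08 Nov 2017 and the protocol Amendment 09 dated on 30 Sep 2020".

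Under the Definitions of DLT and MTD in SAP 3.2.2, the SAP ties the definition to its own table: "The DLTs are defined as any of the toxicities listed in Table 2 occurring during C1 and judged by the investigator as related". In SAP Table 2 all three hepatic criteria name ALT only. The normal-baseline row begins "For subjects with a starting ALT within the normal range for the local laboratory, an elevation ALT" and sets the threshold at 5 × ULN.

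The corresponding row of current protocol Table 2 (Section 9.1.1.1.1) begins "For subjects with a starting AST/ALT within the normal range for the local laboratory, an elevation AST/ALT", with the same 5 × ULN threshold. The other two protocol hepatic criteria also name AST/ALT, as does the DLT table in the synopsis. The text after protocol Table 2 adds: "The only instance in which the AST/ALT and/or bilirubin changes will not be considered a DLT is if there is unequivocal evidence". What must be shown is disease progression as the cause of the rise.

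SAP Section 7 describes the current revision as follows: "SAP amendment 0.2: Efficacy summaries will only include HCC subjects". It goes on to cover efficacy listings and mentions no change to the DLT definition.

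SAP 5.6 and 5.6.2 base the DLT counts and the MTD determination on the DLT Analysis Set. SAP 5.2.1 defines that set by exposure and safety follow-up. None of these sections says which DLT classification feeds the tables.

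**The concern.** Occurrence of DLTs by dose is a primary endpoint (SAP 5.1.1). Its definition in the SAP differs from the one in the protocol version that the SAP names as its base.

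The ALT-only text looks carried forward rather than chosen. The SAP builds on an amendment dated 08 Nov 2017, and the protocol's amendment history (used here only for dating) places the addition of AST in Amendment 08, 28 Aug 2019. Two other SAP passages also keep content that the current protocol no longer has: pERK and CYP7A1 in tumor samples (SAP 3.1.3 against protocol 8.3), and consent within the 28-day screening period (SAP 3.2.4 against protocol 9.1.2.1). The abbreviation note under SAP Table 2 spells out AST, although no criterion in that table uses it.

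SAP Section 5 requires all analyses to follow the SAP, and SAP Section 9 puts derivation rules in separate documents. A programmer who derived DLTs literally from SAP Table 2 would apply a rule other than the one the SRC worked under. The study-report DLT/MTD table could then contradict the record of dose decisions.

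**Working it through.** The plan gives no figure to reproduce on this point. The check is a comparison of texts.

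**Step 1. Hepatic criteria side by side.**

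| Criterion | Protocol Table 2 | SAP Table 2 |
|---|---|---|
| Any baseline | Grade 3 bilirubin (>3.0 × ULN) and/or AST/ALT ≥10 × ULN | Same bilirubin rule and/or ALT ≥10 × ULN |
| Normal baseline | AST/ALT ≥5 × ULN | ALT ≥5 × ULN |
| Abnormal baseline | AST/ALT ≥10 × ULN | ALT ≥10 × ULN |

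AST is named in 3 of 3 protocol criteria and 0 of 3 SAP criteria. The thresholds agree.

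**Step 2. Dating.** From 08 Nov 2017 to 08 Nov 2019 is 730 days; from 28 Aug 2019 to 08 Nov 2019 is 72 days. The SAP's base text therefore precedes the AST addition by 730 − 72 = 658 days.

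**Step 3. Where an AST event lands in the SAP.** Since the SAP hepatic row does not list AST, an AST rise belongs to the row for other adverse events. That row counts related non-hematologic events of Grade 3 or higher, with an exemption: "Isolated CTCAE Grade 3 elevations in biochemistry laboratory values without associated clinical symptoms that last for" at most 7 days. In the protocol the same exemption also sits in the row for events not listed elsewhere, so it does not reach AST, which the hepatic row lists.

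**Step 4. Classify the same event under each document.** Take an AST rise in Cycle 1 of Part 1, judged related, with ALT below its threshold.

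| AST event | Protocol | SAP |
|---|---|---|
| (a) Meets the protocol threshold; Grade 3, isolated, asymptomatic, ≤7 days | DLT (hepatic row) | Exempt |
| Meets the protocol threshold; Grade 4, or Grade 3 and symptomatic or >7 days | DLT (hepatic row) | DLT (other-events row) |
| (b) Abnormal baseline, below 10 × ULN; Grade ≥3 and symptomatic or >7 days | Not a DLT under the hepatic row | Can be a DLT (other-events row) |

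The rules differ in (a) and (b), in opposite directions, and agree in the middle case. Direction (b) is open to enrolled subjects, because inclusion criterion 12 admits AST up to 5 × ULN. It assumes that an AST rise listed in the protocol's hepatic row is not also picked up by the protocol's own other-events row. If it were, (b) would close and (a) would remain.

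**Step 5. Can the AST/ALT rule apply in Part 1?** Protocol 9.1 applies with-food dosing to both parts and sends any further escalation through Section 9.1.1. Escalation cohorts can therefore fall under the AST/ALT rule. How many subjects do is not stated.

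**Step 6. Sensitivity of the table.** The MTD rule allows at most 1 DLT in 6. One reclassified subject moves a cohort between 1/6 (16.7%, the dose can qualify) and 2/6 (33.3%, it cannot). This shows what one subject could do to the reported table; it does not estimate how often that happens.

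**The case against.** The strongest reply is that DLTs will be reported as assigned, not derived. SAP 3.2.2 says that "toxicities assigned as DLTs during the first cycle will be assessed", and SAP 5.6 refers to what the investigators and the Sponsor jointly consider a DLT. Several criteria cannot be programmed at all: relatedness, clinical significance of bleeding, adequacy of anti-emetic treatment, and agreement on Grade 2 events. The classification rule may also sit in the separate programming specifications. ALT-only was the protocol's rule before Amendment 08, so SAP Table 2 is right for subjects treated then. DLT listings and the tabulation of AST by CTCAE grade (SAP 5.6.2 and 5.6.3) would help to expose a discrepancy.

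Most of this stands, and it limits the weight of the point. It does not remove it. In the SAP's definition the investigator judges relatedness, while the list of qualifying toxicities is SAP Table 2. No SAP sentence says that the summaries or the MTD determination use the assigned classification. Unseen specifications do not correct a definition that is out of date in the SAP itself.

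Three stronger readings are tempting and unsupported:

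- **A reader might infer that AST never counts under the SAP.** It can, through the other-events row.
- **A reader might infer that escalation decisions or the chance of escalating are affected.** The SRC works under the protocol, so SAP Table 2 does not enter those decisions.
- **A reader might want an affected AST range or a number of changed DLTs.** Neither document prints AST grade cut-offs or event rates. An interval that started at the protocol threshold would also miss direction (b).

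**Conclusion.** The point holds as a wrong definition in the SAP for a primary endpoint, and it should be fixed. The textual mismatch is certain: all three hepatic criteria differ, and no intended difference is recorded. Its consequence is conditional. It requires that DLTs be derived from SAP Table 2, that a subject treated under the AST/ALT rule have an AST event of type (a) or (b), and that ALT not already settle the classification. If so, the study-report DLT/MTD table can disagree with the SRC record, with the SAP counting fewer DLTs in case (a) and more in case (b). The size cannot be given as a count or a probability from these documents.

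**What to change.** 1. In SAP Table 2, replace ALT with AST/ALT in all three hepatic criteria. Add a footnote that ALT only applies to subjects treated before protocol Amendment 08.
2. In SAP 5.6, add one sentence: DLT summaries and the MTD determination use the DLT classification assigned under the protocol version in force when each subject was treated.

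The cost is one table edit with a footnote and one sentence. No new data are needed.

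Two editorial corrections can be made at the same time; they carry no weight in this point. The bilirubin entry in the protocol synopsis should read Grade 3 (>3.0 × ULN), as in protocol Table 2, instead of a grade above 3. The DLT-evaluability sentence in SAP 3.2.2 should refer to C2 Day 1, as SAP 5.2.1 does, instead of C1 Day 1.

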### 3.2.3 Expansion (Part 2)

Prior to starting Part 2 of the study, the investigators and the Sponsor will use safety, efficacy, PK, and pharmacodynamic data obtained during the Dose Escalation Phase, as well as clinical judgement, to jointly determine the dose schedules to be studied.

During Part 2, the Dose Expansion phase, approximately 40 subjects per dose schedule will be enrolled to examine QD and/or BID dose schedules. Subjects enrolled into Part 2, Dose Expansion phase, must be FGF19-positive as defined by Sponsor-designated laboratory.

When both dose schedules are accruing subjects, an alternating enrollment schema into QD and BID dose schedule will be followed.

### 3.2.4 Subject Participation Phases

The study will be conducted in the following 4 phases: Pretreatment Phase, Treatment Phase, Extension Phase, and Follow-up Phase.

#### **Pretreatment Phase**

Pretreatment Phase will last no longer than 28 days and includes a Screening Period to obtain informed consent and establish protocol eligibility and a Baseline Period to establish disease characteristics before treatment.

#### **Treatment Phase**

Treatment phase will last for 1 treatment cycle of 21 days. Subjects who are receiving study drug at the end of the Treatment Phase will continue to receive study drug in the Extension Phase.

### **Extension Phase**

In the Extension Phase, subjects will continue to receive the same treatment and dose they received during the Treatment Phase, provided termination criteria are not met.

In Treatment and Extension phases, subjects will discontinue study drug at the time of disease progression, development of unacceptable toxicity, withdrawal of consent or termination of the Sponsor. However, subjects may continue to receive study treatment as long as there is demonstrated clinical benefit as judged by the investigator after discussion with the Sponsor or until the end of the study. Disease progression will be determined by the investigator following relevant Response Evaluation Criteria in Solid Tumors (RECIST) 1.1 guidelines for ICC and modified RECIST (mRECIST) for HCC. The mRECIST for this protocol harmonizes the original mRECIST criteria ([Lencioni and Llovet 2010](#)) using triphasic liver computed tomography (CT)/magnetic resonance imaging (MRI; optimized for precontrast, arterial phase, and portal venous phase) and elements of RECIST 1.1 ([Eisenhauer et al., 2009](#)).

### **Follow-up Phase**

After the Off-treatment Visit, all subjects who discontinue study treatment, regardless of their reasons for doing so, will be followed for survival approximately every 12 weeks for up to 12 months or until 6 cycles after last patient in, death, loss to follow-up, or withdrawal of consent, whichever occurs first. Subjects who discontinue study drug without PD (progressive disease) will continue to undergo tumor assessments every 6 weeks until documented PD or another anticancer therapy is initiated.

The data cutoff for the primary analysis will occur once the last subject completes 6 cycles of investigational therapy.

The end of study is defined as when the last ongoing subject completes their off treatment visit.

The schedules of assessments are presented in Table 6 and Table 7 of the Protocol.

## **4 DETERMINATION OF SAMPLE SIZE**

### **Dose Escalation Phase (Part 1)**

It is anticipated that selection of the RP2D will be based on an integrated evaluation of safety, tolerability, clinical benefit, PK, and pharmacodynamic data. The total number of subjects to be enrolled is dependent upon the observed safety profile, which will determine the number of subjects per dose cohort, as well as the number of dose escalations required to achieve the MTD and/or the RP2D. For each dose schedule of QD and BID, assuming 5 dose levels for QD dose schedule and 3 dose levels for the BID dose schedule will be studied and a maximum of 6 subjects will be enrolled per dose level, then between 30 to 48 subjects may be accrued during dose escalation.

### **Dose Expansion Phase (Part 2)**

A total of approximately 40 to 80 subjects will be enrolled in the Dose Expansion phase. Prior to starting the Dose Expansion phase, the investigators and the Sponsor will use safety, efficacy, PK, and pharmacodynamic data obtained during the Dose Escalation Phase, as well as clinical judgement, to jointly determine the dose schedules to be studied.

During Part 2, the Dose Expansion phase, a sample size of 40 evaluable subjects per dose schedule will be enrolled to examine QD and/or BID dosing of H3B-6527 based on the recommended dose determined from Part 1 (Table 3). For a reference of the precision of ORR estimates, the associated 2-sided 95% CIs for ORR up to 30% (40 subjects) are provided in Table 4.

This study makes provision for exploring a BID schedule of H3B-6527 during the Dose Expansion phase if evaluation of the PK, pharmacodynamics, or safety of H3B-6527 suggests that it may be preferable to administer H3B-6527 BID rather than QD. When both dose schedules are accruing subjects, an alternating enrollment schema into QD and BID schedule will be followed.

